8. RESEARCH QUESTION AND OBJECTIVES

Research Question: What are the incidence rates of potential safety events of interest in infants aged 1 month to <1 year and in patients aged 1 to <2 years who were treated with IV pantoprazole in the real-world setting?

Primary Objective: To estimate the incidence of the following outcomes of interest in infants aged 1 month to <1 year and patients aged 1 to <2 years with a diagnosis of GERD with or without EE and treated with IV pantoprazole:

- Agranulocytosis
- Thrombocytopenia
- Leukopenia
- Pancytopenia
- Hypersensitivity (including anaphylactic reactions and anaphylactic shock)
- Hyperlipidaemia
- Hypertriglyceridemia
- Hyponatraemia
- Hypomagnesaemia
- Hypocalcaemia
- Hypokalaemia
- Diarrhea
- Vomiting
- Abdominal distension
- Hepatobiliary injury
- Urticaria
- Angioedema
- Stevens-Johnson syndrome
- Lyell syndrome
- Erythema multiforme
- DRESS
- Tubulointerstitial nephritis
- Photosensitivity
- Peripheral edema
- Injection site thrombophlebitis

Secondary Objective 1: To estimate the incidence of the above-mentioned outcomes of interest in infants aged 1 month to <1 year and patients aged 1 to <2 years treated with IV pantoprazole without a diagnosis of GERD or EE.

Secondary Objective 2: To provide the frequency of the 25 most common diagnostic codes occurring within 30 days prior to starting or on the date of start of IV pantoprazole (ie, index date) through 90 days of the last treatment with IV pantoprazole among infants aged 1 month

090177e1996138d1\Approved\Approved On: 23-Feb-2022 16:44 (GMT)

to <1 year and patients aged 1 to <2 years with a diagnosis of GERD (regardless of EE diagnosis).

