The cut-off of birth weight less than 2.36 kilograms is defined based on a birth weight that is less than third percentile weight for males at birth obtained from Centers for Disease Control and Prevention (CDC) infant weight-for-age charts (available at URL: https://www.cdc.gov/growthcharts/html charts/wtageinf.htm). It is reasonable to assume that infants with birth weight less than 2.36 kilograms are most likely born preterm.

9.3.3. **Subgroups**

Within each cohort (ie, Cohort 1 and 2), 3 subgroups will be identified as follows:

- (1) Patients who have a diagnosis of GERD with EE: defined based on the presence of at least one of the ICD-9-CM or ICD-10-CM codes as shown in Table 1 and the presence of an additional ICD-9-CM or ICD-10-CM code for ulcer of the esophagus during the baseline period or on the index date, as shown in Table 1.
- (2) Patients who have a diagnosis of GERD without EE: defined based on the presence of at least one of the ICD-9-CM or ICD-10-CM codes and no ICD-9-CM or ICD-10-CM code for ulcer of esophagus during the baseline period or on the index date, as shown in Table 1.
- (3) Patients without a diagnosis of GERD or EE: defined as patients who do not have any of the ICD-9-CM or ICD-10-CM codes as shown in Table 1 during the baseline period or on the index date.

ICD-9-CM codes will be used to identify the subgroups prior to October 2015, after which ICD-10-CM codes will be used. No validated algorithm for GERD with or without EE were found to be available via literature review, therefore, a combination of clinical input, and the available codes identified in the literature will be used.² Additionally, there is no explicit ICD-9-CM code for GERD with/without esophagitis. Therefore, based on a cross-sectional study that examined the validity of diagnosis codes of benign upper gastrointestinal disorders using electronic patient records², and an online conversion tool maintained by the Center for Medicare Services and the Centers for Disease Control and Prevention (available at URL: https://icd.codes/convert/icd10-to-icd9-cm), the subgroups of GERD with or without EE will be determined using the operational definitions shown in Table 1:

Table 1. Operationalization of subgroups

Subgroup	ICD-10- CM Code	Description of ICD- 10-CM code	ICD-9- CM Code	Description of ICD-9- CM code

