For analyses of estimation of incidence rates of the outcomes of interest during follow-up, each analysis will be restricted to patients without a history of outcome of interest prior to the index date (ie baseline period); thus, for each analysis of a given specified outcome, a distinct sub-cohort will be used (i.e. for the estimation of the incidence of hepatitis, only patients with prevalent cases of hepatitis in the baseline period will be excluded from follow-up and will not contribute to person-time at risk).

For each outcome of interest, patients will be followed from the index date to whichever of the following occurs first (follow-up period):

- Occurrence of an outcome of interest,
- 90 days following the discontinuation of IV pantoprazole administration,
- Initiation of a separate IV pantoprazole infusion within 90 days following the discontinuation of IV pantoprazole administration, where a separate infusion is defined as the subsequent administration at least 7 days from the end of the previous infusion,
- Death,
- End of enrollment in the database,
- End of study period (ie, 31 December 2020).

Incidence rates of each prespecified outcome of interest will be estimated as the number of patients with a specific outcome of interest during the follow-up period divided by the total person-time at risk and reported as incidence per 1,000 person-years with associated 95% CIs, assuming a Poisson distribution. Exact Poisson confidence limits for the estimated rate are found as the Poisson means, for distributions with the observed number of events and probabilities relevant to the chosen confidence level, divided by time at risk.

$$egin{aligned} Y_l &= rac{\chi^2_{2Y,\;lpha/2}}{2} \ Y_u &= rac{\chi^2_{2(Y+1),\;1-lpha/2}}{2} \end{aligned}$$

- where Y is the observed number of events, Yl and Yu are lower and upper confidence limits for Y respectively, $\chi 2\nu$, a is the chi-square quantile for upper tail probability on ν degrees of freedom.

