For the analysis of the primary objective, incidence rates for all outcomes of interest will be estimated in the overall cohort and in the 2 subgroups, i.e., patients with GERD and EE and patients with GERD, but without EE. Within the overall cohort and in the 2 subgroups, incidence rates will be calculated by duration of IV pantoprazole treatment (<4 days, ≥ 4 days). For the analysis of the secondary objective 1, incidence rates will be estimated for the subgroup of patients treated with IV pantoprazole without a diagnosis of GERD or EE in each cohort and by duration of IV pantoprazole treatment (<4 days, ≥ 4 days) within each cohort. For the analysis of the secondary objective 2, counts of the 25 most common diagnostic codes occurring within 30 days prior to starting or on the date of start of IV pantoprazole (ie, index date) through 90 days of discontinuation with IV pantoprazole in the subsets of patients with a diagnosis of GERD with or without EE will be generated. For each patient, reoccurring codes within 30 days prior to starting or on the date of start of IV pantoprazole (ie, index date) and through 90 days of discontinuation with IV pantoprazole will be counted once.

Detailed methodology for summary and statistical analyses of data collected in this study will be documented in a statistical analysis plan (SAP), which will be dated, filed and maintained

by the sponsor. The SAP may modify the plans outlined in the protocol; any major modifications of primary endpoint definitions or their analyses would be reflected in a protocol amendment.

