More sensitive algorithms will be employed (i.e. algorithms based only on diagnostic codes, rather than more specific algorithms employing procedure and treatment codes in addition to diagnostic codes) for capturing outcomes to ensure safety events of interest are not missed.

However, the limitation of this approach is that, the incidence of some outcomes may be overestimated. Infants with a diagnosis of GERD with EE may be misclassified as those without EE. This is because a confirmed diagnosis of GERD with EE may not be available in infants due to reluctance of healthcare professionals to seek a confirmation via endoscopy. Also, those with a presumptive diagnosis of EE may be classified into the subset of infants with GERD alone. Prior to October 2015, ICD-9-CM codes were exclusively used to identify eligible patients, and GERD is not explicitly captured under this coding schema. ICD-10-CM codes provide additional granularity, but a validated code for erosive esophagitis and GERD is not available, nor well-established or validated in the literature. However, including patients identified using both coding schemes is important to increase sample size of this small population of pediatric patients with a rare condition and exposure. To examine the impact of different coding systems, a sensitivity analysis stratified by those patients identified via ICD-9-CM codes versus ICD-10-CM codes, respectively is planned. The counts of the top 25 most common conditions occurring within 30 days prior to or on the index date through 90 days of the last treatment with IV pantoprazole may include prevalent/comorbid conditions and not just conditions emerging following IV pantoprazole administration. This will however help generate hypotheses about unsuspected safety events in this patient population. Furthermore, a pre-planned sensitivity analysis stratifying by each code type will be performed for the analysis to understand if significant heterogeneity exists in this patient population with respect to the incidence of these outcomes following administration of IV pantoprazole. Finally, the study results may not be generalizable to infants aged 1 month to <1 year and patients aged 1 to <2 years outside of the commercially insured population.

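### The top-25 code list for secondary objective 2 pools pre- and post-treatment codes, so it is poorly suited to the safety-hypothesis use that Section 9.10 gives it

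*Protocol*

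**What the plan says.** Section 8 words secondary objective 2 as a frequency list: "To provide the frequency of the 25 most common diagnostic codes occurring within 30 days prior to starting", the index date included, through 90 days after the last treatment.

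Section 9.8 fixes how the list is made. It calls for "counts of the 25 most common diagnostic codes occurring within 30 days prior to starting or on the date of start of IV pantoprazole", and the window then runs "through 90 days of discontinuation with IV pantoprazole in the subsets of patients with a diagnosis of GERD with or without EE will be generated". Codes that recur in a patient from the start of that window "through 90 days of discontinuation with IV pantoprazole will be counted once". The section states no division at the index date and no removal of codes already present.

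Section 9.3.3 sets who is in the list. The GERD-without-EE subgroup, for example, is "defined based on the presence of at least one of the ICD-9-CM or ICD-10-CM codes and no" code for ulcer of the esophagus, in the baseline period or on the index date. The GERD-with-EE subgroup needs a GERD code and an ulcer code.

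Section 9.10 concedes that the counts "may include prevalent/comorbid conditions and not just conditions emerging following IV pantoprazole administration". The next sentence reads: "This will however help generate hypotheses about unsuspected safety events in this patient population".

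**The concern.** This list is the only analysis in the protocol that looks for events after treatment beyond the prespecified outcomes of Table 3. Section 9.10 gives it a safety use, but the counting rule discards the information that use needs, namely whether a code was there before treatment.

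Ranking adds to the difficulty. Every child is selected on a GERD or esophagitis code and has had IV treatment, so codes for the reasons for treatment and for existing illness can be expected to take many of the 25 places. A new condition in a minority of children has to compete with them on raw frequency. If it does enter, the table does not show how many of its cases are new.

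The incidence analyses in Section 9.8 do guard against this, because "each analysis will be restricted to patients without a history of outcome of interest prior to the index date". The code list has no counterpart to that rule. At stake is how the list may be interpreted, not any incidence rate.

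**Working it through.** The protocol gives no figure for this objective, so there is none to reproduce. The check is of the counting rule itself.

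**Inputs from the protocol**
- Window: 30 days before the index date, the index date, treatment, then 90 days after discontinuation (Section 9.8).
- Rule: each code counts once per patient over that whole window (Section 9.8).
- Population: children with a Table 1 GERD or esophagitis code in the baseline period or on the index date (Section 9.3.3).

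**Inputs assumed**
- N = 1,000 children. The protocol gives neither the size of the GERD subset nor any code frequency.
- p_pre: share of children with the code before or on the index date.
- q_new: share of the remaining children who first receive the code after the index date.
- For simplicity, no earlier records lie outside the 30-day window.

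**Formulas**
- Pooled count = N × [p_pre + (1 − p_pre) × q_new]
- New-onset count = N × (1 − p_pre) × q_new

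| p_pre | q_new | Pooled count | New-onset count |
|---|---|---|---|
| 20% | 0% | 1,000 × 0.20 = 200 | 0 |
| 10% | 11.1% (1/9) | 1,000 × (0.10 + 0.90 × 1/9) = 200 | 100 |
| 0% | 20% | 1,000 × 0.20 = 200 | 200 |
| 60% | 0% | 1,000 × 0.60 = 600 | 0 |
| 60% | 10% | 1,000 × (0.60 + 0.40 × 0.10) = 640 | 40 |
| 60% | 25% | 1,000 × (0.60 + 0.40 × 0.25) = 700 | 100 |

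The first three rows share one pooled count but have 0, 100 and 200 new cases. In the last three rows the code is already common: 100 new cases raise the pooled count only from 600 to 700. The particular values are assumed. That one pooled count fits many different new-onset counts follows from the rule alone.

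**Share of the window before treatment.** With a treatment span of d days, the window is about 30 + d + 90 days. For assumed spans of 1, 4 and 10 days this is 121, 124 and 130 days, so the 30 pre-index days are 30/121 = 25%, 30/124 = 24% and 30/130 = 23% of it. Most of the window falls on or after the start of treatment, but a chronic or admission diagnosis can be coded in any part of it.

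**The case against.** The strongest reply is that the list does what its objective asks. Sections 4 and 8 ask for code frequencies over a window that openly begins before treatment, and Section 9.1 calls the study descriptive with no a priori hypotheses. The safety use is one sentence among the limitations, directly after the mixing is disclosed. All of this stands. A reader might infer that the list cannot serve hypothesis generation at all. The documents do not support that, since an unexpected code with a high count could still prompt follow-up. Poorly suited is the fair description.

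A reader might also infer that the GERD codes will each approach 100% of children because they define the population. This does not follow. Table 1 spreads GERD and esophagitis over seven codes (K21.0, K21.9, 530.10, 530.11, 530.12, 530.19, 530.81), and Section 9.3.3 changes coding system in October 2015. Section 9.8 equates the baseline period with the time before the index date, and the 30 days in Section 9.3.1 are a minimum enrollment. A qualifying code may therefore predate the counting window. It is plausible that these codes rank high, but no percentage can be derived.

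Nor do the documents show that a new event would be kept out of the top 25. That depends on code frequencies they do not give.

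Counting a code once per patient is also normal for a patient-level frequency. The weakness lies only in doing so across the index date.

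Finally, Section 9.8 leaves detailed methods to an SAP that is not at hand, and a breakdown by period could appear there. The pooled window and the counting rule are, however, fixed in the protocol, and so is the claim in Section 9.10.

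**Conclusion.** The point holds in a limited form. The list mixes pre-existing and new conditions in a way that cannot be undone from the table, and this makes it a weak source for the safety hypotheses that Section 9.10 expects from it. The protocol recognises the mixing but offers no remedy and keeps the claim.

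The descriptive objective is met as worded, and the incidence analyses for the primary objective and secondary objective 1 are untouched. The logical conclusion needs no assumption beyond the counting rule. Its numerical size does: the 0-to-200 range per 1,000 is an illustration, not an estimate for this cohort. The change is worth making because it is cheap, not because any planned result is wrong.

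**What to change.** Keep the pooled list. For each code, divide the children it counts into two groups:

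- (a) those with any record of the code before or on the index date, using all available baseline data;
- (b) those whose first record of the code falls after the index date.

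Applied to the children already in the pooled count, (a) and (b) are exclusive and add up to it. The lookback for (a) should not stop at 30 days. Otherwise a child coded 60 days before the index date and again afterwards would either pass as new or fall into neither group.

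Add a second top-25 list ranked by (b). Leave out only the seven GERD and esophagitis codes used for subgroup entry. Keep the ulcer-of-esophagus codes (K22.1 and 530.2), because a first ulcer code after treatment in a child without EE is the kind of event such a list should show.

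Base any hypothesis about unsuspected safety events on list (b). Alternatively, delete that sentence from Section 9.10 and describe the pooled list as morbidity around treatment.

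The cost is one extra table per cohort and a sentence in Section 9.8. Sections 9.7 and 9.9 describe patient-level, dated events already loaded, so no new data are needed. One limit remains: enrollment before the index date may be as short as 30 days, and a first record afterwards may be an old condition coded late. List (b) therefore stays hypothesis-generating.

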9.8.1. Sensitivity Analyses

Two sensitivity analyses will be performed as outlined in Table 6.

Table 6. Sensitivity analyses

Sensitivity Analysis	Description	Rationale
Sensitivity to enforced 30-day enrollment period prior to the index date	Perform analysis in both cohorts without exclusion criteria of at least 30-day enrollment prior to the index date.	Given the age of the study population, patients may not be enrolled in the database for greater than 30 days prior to the index date and it will be important to include such patients in the analysis and examine the incidence rates of outcomes of interest.
Sensitivity to ICD-9-CM versus ICD-10-CM coding for subgroup classification.	Perform analysis in both cohorts, stratified by those patients identified via ICD-9-CM codes versus ICD-10-CM codes, respectively.	ICD-9-CM coding for subgroup identification is less specific than ICD-10-CM based on Lopushinsky et al. 2007 ² . Stratifying incidence rates and comparing incidence estimates between strata will allow to understand comparability between patient cohorts identified using different coding schemes and any potential heterogeneity in patients and incidence rates of outcomes of interest.

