9. RESEARCH METHODS

9.1. Study design

This will be a retrospective cohort study with no comparator group. No a priori hypotheses are specified. Descriptive analyses including an estimation of incidence rates will be performed.

9.2. **Setting**

The study will be conducted using Optum's longitudinal integrated EHR from the US¹, which is described in Section 9.5 This data source includes data from adjudicated administrative insurance claims, inpatient electronic health records, as well as outpatient EHR enabling capture of exposure to IV pantoprazole in the study population of interest. The study period will be defined from 01 January 2007 to 31 December 2020.

9.3. **Study population**

Two separate cohorts, ie, infants aged 1 month to <1 year and patients aged 1 to <2 years will be identified during the study period using the following inclusion and exclusion criteria.

9.3.1. **Inclusion criteria**

Patients must meet all of the following inclusion criteria to be eligible for inclusion in the study:

- 1. At least one administration of IV pantoprazole during the study period from January 1, 2007 to December 31, 2020, and
- 2. For the cohort of infants aged 1 month to <1 year (Cohort 1): Age 1 month to <1 year on the index date (ie, the date of first administration of IV pantoprazole); For the cohort of patients aged 1 to <2 years (Cohort 2): Age 1 to <2 years on the index date.
- 3. Patients must be enrolled in the database for at least 30 days prior to the index date

In addition to this 30-day lookback window, patients will be further excluded based on the occurrence of a history of outcomes of interest identified in Table 3 occurring prior to the index date.

9.3.2. **Exclusion criteria**

Patients meeting any of the following criteria will not be included in the study:

1. Patients with any of the following ICD-9-CM or ICD-10-CM codes occurring prior to or on the index date indicating a preterm birth or birth weight less than 2.36 kilograms will be excluded:

ICD-9-CM codes: 765.01-765.08; 765.10-765.19; 765.21-765.28

ICD-10-CM codes: P07.21-P07.26; P030-P039; P07.01-P07.03; P07.14-P07.18

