9.10. Strengths and limitations of the research methods

This study has several strengths. It is a population-based study, and while the use of IV pantoprazole in infants aged 1 month to <1 year and patients aged 1 to <2 years is rare, this database includes a relatively large number of IV pantoprazole users in these age groups, facilitating generation of precise incidence rates. Given the age of the study population, it is less likely that patients will seek health care outside of the Optum EHR system during the baseline period, and therefore, it is less likely that an outcome of interest occurring during the baseline period will be missed; thus prevalent conditions are unlikely to be mistaken for incident events. Similarly, given the relatively short follow up time, it is less likely that patients will seek care outside of the Optum EHR system during this period, and therefore, that incidence events will be missed.

The study also has several limitations. As is the case in any administrative claims-based study without outcome validation/adjudication, outcome misclassification is a possibility. Diagnosis codes may be incorrect, or may be included as part of the diagnostic rule-out process rather than an indication of diagnosis itself. Conditions not requiring treatment or office visits tend to be systematically undercoded in such databases. It is possible that this study will only capture severe manifestations of such disorders. However, this limitation is likely to be applicable to two outcomes of interest -vomiting and diarrhea as patients experiencing these symptoms may not always visit a physician for care. Another well-recognized limitation of claims database analysis is that the gap between disease onset and date of diagnosis. However, in an incidence analysis, the time at risk begins on the date of IV pantoprazole administration (ie index date), not at disease onset. For outcome events, as only the incidence of new events is considered that occur after the initiation of IV pantoprazole, the impact of this limitation is expected to be minimal, as complications arising in infants would almost certainly be captured in the inpatient setting. Additionally, this would result in underestimating the incidence rate as time at risk would be inflated.

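### Exclusions that reach back to birth rest on a guaranteed record of only 30 days, and the one lookback sensitivity analysis loosens that minimum instead of testing it

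*Protocol*

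**What the plan says.** Protocol 9.3.1, criterion 3, applies to both cohorts: "Patients must be enrolled in the database for at least 30 days prior to the index date". The cohorts are defined by "Age 1 month to <1 year on the index date" (Cohort 1) and "Age 1 to <2 years on the index date" (Cohort 2).

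Two exclusions look further back than 30 days. Section 9.3.2 removes children with codes "occurring prior to or on the index date indicating a preterm birth or birth weight less than 2.36 kilograms". The end of 9.3.1 adds: "In addition to this 30-day lookback window, patients will be further excluded based on the occurrence of a history of outcomes of interest". Section 9.8 repeats the outcome rule analysis by analysis and equates the baseline period with the time before the index date. It gives that period no length or starting point, and no section requires enrolment from birth.

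Table 6 in 9.8.1 lists two sensitivity analyses; the second concerns ICD-9-CM against ICD-10-CM coding. The first, the only one on lookback, repeats the analysis in both cohorts without the 30-day rule. Its reason begins: "Given the age of the study population, patients may not be enrolled in the database for greater than 30 days".

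Section 9.10 lists as a strength that care outside the system during the baseline period is improbable, and concludes: "thus prevalent conditions are unlikely to be mistaken for incident events".

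**The concern.** Preterm birth and low birth weight are facts about birth, and their codes belong mainly to the birth period. A prior-outcome exclusion works only over the time that is on record. A child who enters the database at 17 months and is treated at 18 months satisfies criterion 3, although a preterm code or an outcome code from the first 17 months may never be seen. Such a child stays in the cohort, and a persisting or recurring condition coded after the index date counts as a new event.

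The study estimates absolute incidence rates without a comparator (9.1), so an error of this kind cannot cancel between groups. Several outcomes in Table 3 can persist or recur, such as the chronic liver disease codes, vomiting and diarrhea. The useful check is whether rates change when more history is required. The plan checks only what happens when less is required.

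**Working it through.** **The protocol's own figures.** The protocol gives no distribution of enrolment length. Its only computed statistical figures are the Wilson limits in Table 5, and all 12 rows reproduce to four decimals from the rounded event counts. For example, 75 of 7,489 gives 0.0080 to 0.0125, as stated. They do not bear on lookback, but one serves as a yardstick in step 4.

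**1. Share of life guaranteed on record.** Inputs: the 30-day minimum and the cohort ages (9.3.1). Formula: min(1, 30 / age in days). Time that may be unseen: age minus 30 days.

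| Age at index (days) | Guaranteed share | May be unseen (days) |
|---|---|---|
| 30 | 100% | 0 |
| 60 | 30/60 = 50% | 30 |
| 182 | 30/182 = 16.5% | 152 |
| 365 | 30/365 = 8.2% | 335 |
| 547 | 30/547 = 5.5% | 517 |
| 730 | 30/730 = 4.1% | 700 |

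The guarantee runs from 100% down to about 8% of prior life in Cohort 1, and from about 8% down to 4% in Cohort 2. If age is uniform within each cohort (assumption), the mean guaranteed share is about 23% and 5.7%. These are floors for a child with exactly 30 days, not averages of what will be observed.

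**2. Whom the age reason fits.** A Cohort 2 child is at least 365 days old, so age cannot prevent 30 days of enrolment. In Cohort 1, an infant aged 30 days cannot have more than 30. Under uniform age from 30 to 364 days (335 values), that is 1/335 = 0.3%; taking one month as 28 days, it is 3/337 = 0.9%. An infant of 5 to 8 weeks who was enrolled some time after birth can also fall short. Ages up to 60 days make up 31/335 = 9.3% under the same assumption. Above that age, a short record comes from late enrolment.

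**3. What row 1 adds.** It adds children with fewer than 30 days of enrolment. In Cohort 2, with a single enrolment span, each has at least 365 − 29 = 336 days (about 11 months) of life before enrolment. These are the children for whom the exclusions have least to work on. If the rates change, the change mixes a different set of patients with poorer history. If they do not, nothing has been learned about whether 30 days is enough.

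**4. Possible size (illustration; inputs assumed).** Let u be the share of a cohort with an unseen prior outcome and r the share of those coded again in about 93 days of follow-up. Spurious rate per 1,000 person-years = 1,000 × u × r × 365.25/93.

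- u = 1%, r = 25%: 1,000 × 0.0025 × 3.927 = 9.8, or about 19 events in Cohort 1 (7,489 × 0.0025) and 17 in Cohort 2 (6,657 × 0.0025).
- u = 10%, r = 50%: 1,000 × 0.05 × 3.927 = 196, or about 374 and 333 events.

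Yardstick: at a frequency of 0.01 in Cohort 1, the Table 5 half-width is (0.0125 − 0.0080)/2 = 0.00225. The low case adds a frequency of 0.0025, about as much as that half-width. The protocol supplies neither u nor r.

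**5. The 9.10 argument.** It concerns care sought elsewhere during the baseline period. A child not yet enrolled is a different case, and neither the strengths nor the limitations mention it.

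**The case against.** The strongest reply is that 30 days is a floor. The preterm rule and the outcome-history rule take whatever record exists, so a child with a long record is screened on all of it. This stands. A reader might infer that the study looks back only 30 days, but 9.3.1 and 9.8 say otherwise. The percentages in step 1 describe the worst admissible case, and the number of children near it is unknown.

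A reader might also infer that the eligibility ages contradict the Table 6 reason outright. They do not. It is true for infants of about one month and plausible for those a few weeks older. It is too broad, because it is applied to both cohorts.

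A third tempting inference is that the GERD/EE subgroups also need the child's whole earlier life. Section 9.3.3 counts codes in the baseline period or on the index date, and the length of that period is not stated. A child treated for current GERD can be classified from index-date codes, so the documents do not support extending the point that far.

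Unseen time is itself partly an assumption. The data are linked EHR and claims (9.5), and the protocol does not say whether EHR entries from before enrolment are used. A child with an earlier, lapsed enrolment may also have older records. Nor is an acute episode months earlier the same as a prevalent condition at index, so a count of children with some earlier episode does not measure bias in a rate.

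Finally, row 1 asks what excluding short-enrolled children does and does not claim to validate the 30 days. That is fair, and it is a reason to keep row 1. It leaves the other question without any planned analysis, while 9.10 states the answer. The analysis plan may add detail, but the enrolment rule, the direction and reason of Table 6 and the 9.10 statement are fixed in the protocol.

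**Conclusion.** The point holds in a limited form. The preterm/low-birth-weight and prior-outcome exclusions reach back over all earlier life, while criterion 3 guarantees as little as 8% of it at 12 months and 4% near 24 months. The only lookback sensitivity analysis weakens that guarantee, so it cannot show whether 30 days is enough. Its age reason fits the youngest Cohort 1 infants and no Cohort 2 child. The 9.10 statement on prevalent conditions is untested for life before enrolment.

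The effect on the rates cannot be computed from the protocol. The range of about 10 to 196 per 1,000 person-years in the illustration rests wholly on assumed shares and a 93-day follow-up. It shows that the effect could matter, not that it does. The reading of pre-enrolment life as unseen assumes a single enrolment span and no use of earlier EHR entries. This does not invalidate the main analysis; it is an inexpensive check that the plan should contain.

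**What to change.** 1. Table 6, row 1: keep the analysis in both cohorts, limit its age reason to the youngest Cohort 1 infants, and report the added patients as their own stratum in each cohort. Narrowing row 1 itself to infants enrolled within 30 days of birth would not serve. Together with fewer than 30 days before index, that leaves only infants under about 60 days and removes Cohort 2.
2. Table 6, new row: in both cohorts, repeat the analysis in children whose enrolment starts around birth, for example within 30 days. Age is derived from birth week (9.4.3.1), so the margin is exact only to about a week.
3. Report the distribution of pre-index enrolment in each cohort. This gives the missing size of the problem.
4. Section 9.10: make the statement on prevalent conditions conditional on the analysis in item 2 agreeing with the main result.

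Cost: one added run, one extra stratum and one descriptive table, from data and measures already planned. The birth-enrolled set is smaller, especially in Cohort 2, so its intervals will be wider and agreement there will be weaker evidence. These children may also differ from late enrollers in other ways, so a difference would be a warning rather than a measure of the bias. The main cohorts and the main analysis do not change.
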